7. REFERENCES

- 7.1 NON-STANDARD STATISTICAL METHODS
- 7.2 DATA MANAGEMENT PLAN S:/Centre for Trials Research/Research/Mixed Studies/DOMINO/eTMF/8.0 Data Management & Statistics\8.1 Data Management\8.1.1 Data Management Plan
- 7.3 STUDY MASTER FILE AND STATISTICAL MASTER FILE S:/Centre for Trials Research/Research/Mixed Studies/DOMINO/eTMF S:/Centre for Trials Research/Research/Mixed Studies/DOMINO/eTMF/8.0 Data Management & Statistics/8.5 Statistics
- 7.4 OTHER SOPS OR GUIDANCE DOCUMENTS

SAP DEVIATION LOG

Document number:	Document version:	
Reason for deviation:	-	

8. APPENDICES

Appendix A: Developing a Mediterranean Diet Index (MDI)

The MDI is a score (Trichopoulou A, Costacou D, 2003) taking integer values ranging from 0 to 9. It consists of nine components, each of which contributes either 0 (if the condition is not met) or 1 (if the condition is met). Table 2 reports the nine categories and when 1 point for each category is assigned. The MDI is the sum of the nine components. In (Trichopoulou A, Costacou D, 2003) adherence to a Mediterranean diet was classified as low for individuals with scores 0-3, moderate for individuals with scores 4-5, and high for those with score 6-9. Based on this classification, the lifestyle factor "diet" could be either dichotomised as high adherence to MD (MDI score 6-9) or non-high (MDI score 0-5), or used as a categorical covariate (with three levels), and PS and balancing weights computed for a treatment variable with three factors.

```
TPL/008/2(v1.0)
```

DOMINO-HD:	STATISTICAL ANALYSIS PLAN	

Table 2: The nine categories of foods included in the diet indices. *The ratio of polyunsaturated to saturated fatty acids is computed based on the standard reference values of polyunsaturated and saturated fatty acids included in the foods the individuals report to consume per week. **This corresponds to 2(1) glass(es) of wine or beer for men(women).

Category	Food category	Condition to obtain 1 point (for MDI)
1.	Vegetables	1 consuming ≥ sex-specific sample median (per week)
		0 consuming < sex-specific sample median (per week)
2.	Legumes	1 consuming ≥ sex-specific sample median (per week)
		0 consuming < sex-specific sample median (per week)
3.	Fruits and nuts	1 consuming ≥ sex-specific sample median (per week)
		0 consuming < sex-specific sample median (per week)
4.	Cereal	1 consuming ≥ sex-specific sample median (per week)
		0 consuming < sex-specific sample median (per week)
5.	Fish	1 consuming ≥ sex-specific sample median (per week)
		0 consuming < sex-specific sample median (per week)
6.	Diary	0 consuming ≥ sex-specific sample median (per week)

TPL/008/2(v1.0)

Canolfan Ymchwil Treialon

DOMINO-HD: STATISTICAL ANALYSIS PLAN

		1 consuming < sex-specific sample median (per week)
7.	Meat and poultry	0 consuming ≥ sex-specific sample median (per week) 1 consuming < sex-specific sample median (per week)
8.	Alcohol consumption	0 otherwise1 for consumption of 10-50g per day for men, and 5-25g per day for women**
9.	Unsaturated to saturated fatty acids ratio*	0 otherwise 1 for ratio higher than the sex-specific sample median

The computation of each individual score for categories 1-8 (whether one or zero is assigned) uses the average number of servings per week consumed for each participant. For the computation of each individual's unsaturated to saturated fatty acids ratio, the total sum of unsaturated and the total sum of saturated fatty acids per week is used.

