We will derive a Mediterranean Diet Index (MDI) as defined by (Trichopoulou et al., 2003). This index's values range from 0 to 9, with higher values indicating higher adherence to an MD. The final score is the sum of nine elements, each of which is either 0 or 1. Beneficial components (namely 1. vegetables, 2. legumes, 3. fruits and nuts, 4. cereal, and 5. fish) contribute one point if their consumption is above the sex-specific sample median. For non-beneficial components, (6. dairy, 7. meat and poultry) one point is assigned to those whose consumption is below the sex-specific sample median. Finally, for alcohol consumption (8.), one point is assigned to men who consume between 10 and 50 g per day and to women who consume between 5 and 25 g a day. Finally, to score lipid intake, the unsaturated to saturated fatty acids (9.) ratio is calculated and one point assigned if the ratio exceeds the sex-specific sample median. A full description of the definition of the MDI is in Appendix A.

Additionally, the Healthy Eating Index (HEI) will be used as a diet score. Its values range from 0 to 100, with higher values representing better eating habits. The final score is a sum of 13 components, nine categories of adequate eating, and four moderators. A full description of the definition of the HEI is in Appendix B.

Both MDI and HEI will be used (one at a time) to assess the sensitivity of our findings. Additionally, the two scores will be compared as to their effect on the progression of HD – unless one is dropped (see section 6.2.3).

3. Physical activity:

Step counts over a 6-week period from the baseline assessment will be extracted from each participant's FitBit. 5000 steps per day (Tudor-Locke et al., 2013) will be used as a threshold to dichotomise participants into sedentary (< 5000 steps per day) and active (\geq 5000 steps per day).

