Appendix B: Developing a Healthy Eating Index (HEI)

The HEI is a score (Krebs-Smith et al., 2018) ranging from 0 to 100. It consists of 13 components, each of which contributes any value from 0 to 5 or 10 (depending on the component), with the maximum value (5 or 10) representing the best eating behaviour for each component. Table 3 reports the 13 categories, and the condition for the minimum/maximum points to be assigned for each category. The HEI is the sum of the nine components. To dichotomise the HEI, we will use 59 as a cut-off – higher values will be assigned 1, and 0 otherwise. Further, 79 could be used as a second cut-off point to trichotomise (if desired). If no or very few observations score over 59, then the median of the sample will be used as threshold for dichotomisation.

TPL/008/2(v1.0)

Centre for Trials Research Canolfan

Ymchwil Treialon

Table 3: The 13 categories of foods included in the HEI. *Ratio of poly- and monounsaturated fatty acids (PUFAs and MUFAs) to saturated fatty acids (SFAs).

Component	Maximum	Standard for	Standard for minimum
-	point	maximum score	score of zero
Adequacy:			
Total fruits	5	≥0.8 cup equiv. per 1000kcal	No fruits
Whole fruits	5	≥0.4 cup equiv. per 1000kcal	No whole fruits
Total vegetables	5	≥ 1.1 cup equiv. per 1000kcal	No vegetables
Greens and beans	5	≥ 0.2 cup equiv. per 1000kcal	No dark green vegetables or legumes
Whole grains	10	≥1.5 oz equiv. per 1000kcal	No whole grains
Dairy	10	≥1.3 cup equiv. per 1000kcal	No dairy
Total protein foods	5	≥2.5 oz equiv. per 1000kcal	No protein foods
Seafood and plant proteins	5	≥0.8 oz equiv. per 1000kcal	No seafood or plant proteins
Fatty acids*	10	(PUFAs+MUFAs)/SFAs	(PUFAs+MUFAs)/SFAs
		≥2.5	≤1.2
Moderation:			
Refined grains	10	≤1.8 oz equiv. per 1000kcal	≥4.3 oz equiv. per 1000kcal
Sodium	10	\leq 1.1 grams per 1000kcal	≥2 grams per 1000kcal

TPL/008/2(v1.0)

DOMINO-HD: STATISTICAL ANALYSIS PLAN

Added sugars	10	≤6.5% of energy	≥26% of energy
Saturated fats	10	≤8% of energy	≥16% of energy

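### The Mediterranean Diet Index is scored on raw weekly servings with no allowance for energy intake, so within each sex it partly measures how much a participant eats; the HEI does not

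*SAP*

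**What the plan says.** SAP section 6.2 (Diet) and Appendix A build the MDI from nine items worth 0 or 1. The five beneficial foods (vegetables, legumes, fruits and nuts, cereal, fish) "contribute one point if their consumption is above the sex-specific sample median". Table 2 writes the same rule as at or above the median; the handling of ties does not matter here. Dairy, and meat and poultry, earn the point when consumption is below that median. The text under Table 2 says that scoring of categories 1-8 "uses the average number of servings per week consumed for each participant"; this point concerns categories 1-7. Item 9 is a fatty acid ratio, "1 for ratio higher than the sex-specific sample median". Appendix A classes scores of 6-9 as high adherence and 0-5 as non-high, and Table 4 carries the same cut into the LifeHD score.

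Appendix B scores the HEI from the same food frequency questionnaire (FFQ). Ten of its 13 components are amounts per 1000 kcal (total fruits, for example, at "≥0.8 cup equiv. per 1000kcal"), two are shares of energy (added sugars at "≤6.5% of energy"), and one is a fatty acid ratio.

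Section 6.2 uses the two indices one at a time to test sensitivity and compares their effects on progression. The adjustment sets in sections 6.2.1 and 6.2.2 draw on the other lifestyle factors, the baseline outcome, age and HD stage. Appendix C, Step 1 adds sex, time since diagnosis and follow-up time. None contains energy intake.

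**The concern.** An index of dietary pattern should separate people by what they eat. Here five items move up with quantity and two move down, so total intake leaves a net upward pull on the score. Sex-specific medians remove the average difference between men and women but not the variation within each sex.

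Two things are at stake. First, the MDI and HEI are treated as alternative measures of one exposure, yet only the MDI depends on total intake. If they disagree, the plan cannot tell diet pattern from quantity. Second, intake could be related to disease. Section 5.5.1 summarises malnutrition (MUST) and swallowing difficulty (EAT-10) at baseline, but neither enters a model, and cUHDRS contains no nutritional or swallowing measure. If intake falls with severity, the diet estimate may carry confounding that the planned covariates do not capture. The same MDI can also serve as a confounder in the sleep and activity models and as a component of LifeHD.

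**Working it through.** The SAP states no figure for this, so there is nothing of its own to reproduce. The direction follows from Table 2; the size needs assumptions.

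**Direction.** Multiply all food amounts by the same factor above 1. Items 1-5 can only gain points, items 6-7 can only lose them, and item 9 is unchanged. Item 8 (alcohol) is a range and has no fixed direction. Net pull: 5 − 2 = 3 items upward.

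**Assumptions (not from the SAP), within one sex.** Log servings of each of seven foods = e + f, where e is log total intake (mean 0, SD s_e, normal) and f is an independent food-specific term (mean 0, SD s_f, normal). Composition is therefore unrelated to intake. The alcohol point has probability 0.2 and the fat-ratio point 0.5, both independent of intake.

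**Closed-form check.** For a given e, the chance of being at or above the median of a food is Φ(e/s_f). With s_e = 0.3 and s_f = 0.6:

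- One SD above average intake: Φ(0.5) = 0.691. Expected MDI = 5 × 0.691 + 2 × 0.309 + 0.2 + 0.5 = 4.8.
- One SD below: Φ(−0.5) = 0.309. Expected MDI = 5 × 0.309 + 2 × 0.691 + 0.7 = 3.6.

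**Simulation (300,000 draws per case), thirds of intake.**

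| s_e | s_f | MDI 6-9, lowest third | MDI 6-9, highest third | Correlation of MDI with log intake |
|---|---|---|---|---|
| 0.2 | 0.8 | 13% | 25% | 0.20 |
| 0.3 | 0.6 | 9% | 31% | 0.36 |
| 0.3 | 0.5 | 7% | 33% | 0.41 |

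In the middle row, mean MDI is 3.6 in the lowest third and 4.8 in the highest. The first and last rows are the weakest and strongest cases over s_e 0.2-0.3 and s_f 0.5-0.8.

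**Wider assumptions.** With a coefficient of variation of intake of 0.2-0.4, s_f 0.4-0.8 and an alcohol probability of 0.3, the range runs from 15% versus 28% to 5% versus 45%, with correlation 0.19-0.54.

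**Scored per unit of energy.** The e term cancels, so each food item has probability 0.5 at every intake. Combining the seven foods with the fat-ratio item gives eight items at 0.5: P(≥6 of 8) = 37/256 = 0.145 and P(≥5 of 8) = 93/256 = 0.363. Then P(MDI 6-9) = 0.8 × 0.145 + 0.2 × 0.363 = 0.19 in every third, and the correlation is 0.

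**The case against.** - **Source.** The MDI is adopted from a cited publication together with its 6-9 cut-off, and choosing quantity or density is a design decision. This stands as a reason to keep the raw score in the analysis. It does not remove the dependence on intake in this cohort, or the mismatch with the HEI.
- **An energy-independent exposure is already planned.** The HEI analysis is a check of a kind, and section 6.2.4 states no preference between the indices. They also differ by design: dairy earns up to 10 HEI points and costs an MDI point, so energy scaling would not make them equivalent. That stands, and it is too strong to say that the comparison is undermined. Scaling would remove one avoidable source of disagreement.
- **Existing controls.** Sleep, activity, the baseline outcome, age and HD stage enter the models to varying degrees, and OVtool or E-values probe unmeasured confounding. These narrow a severity pathway, but they do not take quantity out of the score.
- **Standing of the analysis.** The primary objective is feasibility, and the diet effects on cUHDRS are secondary and exploratory. This limits the weight of the point.

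A reader might go further and infer that sicker participants eat less, score low because of disease, and so bias the diet effect on cUHDRS. The SAP does not support that as a finding. It reports no intake, MUST or EAT-10 results, and the calculation above contains neither severity nor outcome. Bias would require intake to predict the 12-month outcome after the planned adjustment.

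**Conclusion.** The point holds as one about how the exposure is scored. Table 2 and the servings-per-week rule make the MDI rise with quantity eaten at unchanged composition, every HEI component is independent of total intake, and no planned model removes the difference. The word *partly* matters: two items pull the other way and the fat ratio is neutral.

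Under the main assumptions, high adherence is about 7-13% in the lowest third of intake and 25-33% in the highest. Intake accounts for about 4-17% of the variance in MDI (0.20² to 0.41²). The direction rests on the SAP alone; these sizes rest on assumed distributions. Confounding by disease severity is plausible, but its size and direction are not shown. For a secondary, exploratory analysis this is an inexpensive improvement and does not invalidate the plan.

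**What to change.** In Appendix A, also score categories 1-7 on servings per 1000 kcal, against the sex-specific sample median of that density. The energy figure comes from the FFQ and is already needed for the HEI. Report the diet analyses with both the density and the raw-servings MDI, and use the density version for the MDI-HEI comparison.

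Where only the raw MDI is used, add energy intake to the outcome regression and not to the balancing weights. Section 6.1.1 cites 60-80 observations per covariate per group. If about 19% of 300 participants score 6-9, the high group has about 0.19 × 300 = 57, which is short of the guidance for even one covariate. Energy would compete there with age and HD stage. Density scoring uses no balancing covariate.

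The cost is SAP wording, scoring code and one extra analysis, with no new data. The downside is a departure from raw-servings scoring while keeping the cited 6-9 cut-off, which the SAP should state openly.

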Appendix B: Developing a Healthy Eating Index (HEI)

The HEI is a score (Krebs-Smith et al., 2018) ranging from 0 to 100. It consists of 13 components, each of which contributes any value from 0 to 5 or 10 (depending on the component), with the maximum value (5 or 10) representing the best eating behaviour for each component. Table 3 reports the 13 categories, and the condition for the minimum/maximum points to be assigned for each category. The HEI is the sum of the nine components. To dichotomise the HEI, we will use 59 as a cut-off – higher values will be assigned 1, and 0 otherwise. Further, 79 could be used as a second cut-off point to trichotomise (if desired). If no or very few observations score over 59, then the median of the sample will be used as threshold for dichotomisation.

TPL/008/2(v1.0)

Centre for Trials Research Canolfan

Ymchwil Treialon

Table 3: The 13 categories of foods included in the HEI. *Ratio of poly- and monounsaturated fatty acids (PUFAs and MUFAs) to saturated fatty acids (SFAs).

Component	Maximum	Standard for	Standard for minimum
-	point	maximum score	score of zero
Adequacy:			
Total fruits	5	≥0.8 cup equiv. per 1000kcal	No fruits
Whole fruits	5	≥0.4 cup equiv. per 1000kcal	No whole fruits
Total vegetables	5	≥ 1.1 cup equiv. per 1000kcal	No vegetables
Greens and beans	5	≥ 0.2 cup equiv. per 1000kcal	No dark green vegetables or legumes
Whole grains	10	≥1.5 oz equiv. per 1000kcal	No whole grains
Dairy	10	≥1.3 cup equiv. per 1000kcal	No dairy
Total protein foods	5	≥2.5 oz equiv. per 1000kcal	No protein foods
Seafood and plant proteins	5	≥0.8 oz equiv. per 1000kcal	No seafood or plant proteins
Fatty acids*	10	(PUFAs+MUFAs)/SFAs	(PUFAs+MUFAs)/SFAs
		≥2.5	≤1.2
Moderation:			
Refined grains	10	≤1.8 oz equiv. per 1000kcal	≥4.3 oz equiv. per 1000kcal
Sodium	10	\leq 1.1 grams per 1000kcal	≥2 grams per 1000kcal

TPL/008/2(v1.0)

DOMINO-HD: STATISTICAL ANALYSIS PLAN

Added sugars	10	≤6.5% of energy	≥26% of energy
Saturated fats	10	≤8% of energy	≥16% of energy

Appendix C: LifeHD score

Table 4 reports the covariates which will be included in the LifeHD index. The following algorithm describes the development of the score.

- Step 1. The risk factors will first be included separately in a regression model (together with non-lifestyle factors: age, sex, HD stage, time since diagnosis, and follow-up time since last visit). We will use a linear or logistic regression model, depending on the outcome (continuous or binary). This will also enable us to understand the impact of each category on the outcome variable and define the reference category for each factor. For diet, the sign and magnitude of each category will allow us to understand the most and least beneficial clusters thus the beneficial category is group 1, and the other category is 0. The least beneficial cluster will be the reference category to another (group 1 or higher for more than two categories) will increase the index thus, higher values of the index indicate "better" lifestyle.
- Step 2. Factors that were significant in the first step will be simultaneously placed into a single regression model linear or logistic regression depending on the outcome. (For DOMINO-HD, as the outcome is cUHDRS or its components linear regression will be used.)
- Step 3. From the final regression models of step 2, risk scores will be assigned for each factor with the respective β coefficients (steps 4 and 5).
- Step 4. All β coefficients will be standardised so that the lowest one has a value of 1 this is achieved by multiplying every β coefficient with 1/minimum(β).

TPL/008/2(v1.0)

DOMINO-HD: STATISTICAL ANALYSIS PLAN

Step 4b.	(optional) Rounding each coefficient to the closest integer. In this case,
	all individual scores are positive integers. This will enable easier
	calculaiton of the scores, and higher values of the score would indicate
	better "lifestyle".

Step 5. The risk score for an individual will be obtained by summing the scores for the appropriate level of each of the risk factors.

Correlation and association of LifeHD with the outcome and the lifestyle factors under study (diet, sleep, physical activity) will be tabulated.

Variable	Calibration
Diet*	MDI: 0-5; 6-9
	HEI: 0-59; 60-100
Sleep*	SE > tertile/quantile
	$SE \leq tertile/quantile$
Physical activity*	MET > tertile
	$MET \leq tertile$
BMI*	$BMI \le 25 \text{ normal}$
	$25 < BMI \le 30$ overweight
	BMI > 30 obese
Age**	< 47 years old
	47 – 53 years old
	\geq 53 years old
CAG repeat length**	35 < CAG < 42
	$CAG \ge 42$

Table 4: Lifestyle factors included in LifeHD. *Modifiable; **Non-modifiable

TPL/008/2(v1.0)

Canolfan Ymchwil Treialon

DOMINO-HD: STATISTICAL ANALYSIS PLAN

HD stage**	Participants could be either in stage:	
	- Late pre-manifest (LPM): No motor onset, age \geq 18yrs, CAG \geq 36, CAP $>$ 80	
	- Stage 1: 10 < TFC ≤ 13	
	- Stage 2: 6 < TFC ≤ 10	
	- Stage 3: TFC ≤ 6	
Antidepressant	Use; or	
medication*	No use	

Canolfan **Ymchwil Treialon**

DOMINO-HD:	STATISTICAL ANALYSIS PLAN	

Table 5: Definition of variables/outcomes

Outcome/definition	Scale(s)	Timingofmeasurements	Score range	Interpretation
	Age	At baseline		The age of the participant at the time of the baseline assessment
	HD stage	At baseline	LPM, stage 1, 2, 3	The HD stage of the participant at the beginning of the study
	CAG	At baseline		The length of CAG repeat of the participant
	САР	At baseline		The CAP score of the participant at the beginning of the study
	Sex	At baseline		The sex of the participant as specified at birth
Severity of the disease	cUHDRS	At baseline and 12 months after baseline		Measure of the severity of the disease at the baseline assessment

TPL/008/2(v1.0)

Page 30 of 41

CAERDY

Canolfan Ymchwil Treialon

DOMINO-HD: STATISTICAL ANALYSIS PLAN

				and at the time of the follow-up assessment. Higher values indicate less severe impairment.
Severity of the disease – motor	TMS	At baseline and 12 months after baseline	0-124	Lower values indicate less severe impairment
Severity of the disease – functional	TFC	At baseline and 12 months after baseline	0-13	Higher values indicate less severe impairment
Severity of the disease – cognitive	SDMT	At baseline and 12 months after baseline	Raw number of correct answers	Higher values indicate less severe impairment
Severity of the disease – cognitive	SWRT	At baseline and 12 months after baseline	Raw number of correct answers	Higher values indicate less severe impairment
Sleep quality	Total minutes of sleep	At baseline	Time (in minutes)	Average (over one week) minutes of sleep per day
Sleep quality	Sleep efficiency	At baseline		The ratio of total minutes of sleep to time in bed

PRIFYSGOL CAERDYD

Canolfan Ymchwil Treialon

DOMINO-HD: STATISTICAL ANALYSIS PLAN

Adherence to Mediterranean diet	MDI score	At baseline	0-9	Higher values indicate better adherence to Mediterranean diet
Adherence to a healthy diet	HEI score	At baseline	0-100	Higher values indicate healthier diet
Physical activity	Step count	At baseline	Raw number of steps per day	Average (over one week) number of daily steps
Physical activity	MET-minutes	At baseline		A MET is the ratio of a person's working metabolic rate relative to their resting metabolic rate (one MET is the energy spent sitting at rest). Higher values indicate more active lifestyle.
	BMI	At baseline	Raw number	 ≤ 25 normal 25 < BMI ≤ 30 overweight > 30 obese
Lifestyle undex	LifeHD	At baseline		Higher values indicate a better overall lifestyle (better adherence to

TPL/008/2(v1.0)

Canolfan Ymchwil Treialon

DOMINO-HD:	STATISTICAL ANALYSIS PLAN

				a healthy diet, sleep schedule, and physical activity)
Total FitBit wear time	Total wear hours	Throughout the study	Time (in minutes)	Adherence to wearing the FitBit. Higher values indicate better (more consistent) usage of the tracker.

Canolfan Ymchwil Treialon

DOMINO-HD: STATISTICAL ANALYSIS PLAN

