6.1.5 TIMING, UNITS AND DERIVATION OF SECONDARIES

The secondary outcomes (cUHDRS, TMS, TFC, SWRT and SDMT) will be assessed 12 months after the initial (baseline) assessment.

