A MET-minute is the amount of energy expended during a minute while at rest. It is a ratio of a person's working metabolic rate relative to their resting metabolic rate (one MET is the energy spent sitting at rest for one minute). As there is no evidence in the literature about a clear distinction between active and inactive lifestyle for individuals with HD, participants in the lowest tertile (\leq 33%) will be classified as inactive (Schiepers et al., 2018). MET-minutes will be extracted from FitBit. MET-minutes will be used as an alternative measure of physical activity (if available) to assess the sensitivity of our findings.

Construction of LifeHD score:

A LIBRA style index (Anstey et al., 2013; Kivipelto et al., 2006; Schiepers et al., 2018) will be created to investigate the association of a lifestyle-based score with the progression of HD

TPL/008/2(v1.0)

DOMINO-HD: STATISTICAL ANALYSIS PLAN

(as measured by cUHDRS and its four components). This will be called LifeHD. Modifiable lifestyle factors will be included, namely:

- Sleep;
- Diet;
- Physical activity;
- BMI.

Additionally, the following non-modifiable measures will be included:

- Age group (< 47yrs, 47 53yrs, > 53yrs);
- CAG repeat length;
- HD stage.

To achieve the scoring sums (LifeHD scores), the steps in Appendix C will be followed.

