6.2.2 COVARIATE ADJUSTMENT

Unweighted analyses (using regression models) will control for age, HD stage, as well as baseline values for the outcomes. Additionally, we will control for the two lifestyle (the continuous version of these) factors not included in each case.

The primary goal is to control for confounding bias, using PS and balancing weights (Markoulidakis, Taiyari, et al., 2021), for the two lifestyle factors other than the one under study in each case. Expecting limitations due to the restricted sample size (Markoulidakis, Holmans, et al., 2021), we will attempt to balance additionally for age, HD stage, and baseline values of the outcome.

The outcome analysis will also be performed using the LifeHD score constructed, as a categorical covariate, with and without the use of PS and balancing weights. The LifeHD score will be used both in addition to the individual lifestyle factors (e.g. using LifeHD score as 'treatment', and the three lifestyle factors as confounders), and solely – without taking into consideration the other lifestyle factors.

Outcome will be standardised, so that we report standardised effect sizes. The estimand of interest (e.g. ATE or ATT) will be determined based on whether adequate balance is achieved or not. If we are unable to achieve adequate balance, then unweighted regression and means difference will be reported.

Additionally, significance tests for difference of means of the covariates we wish to control for and the outcome will be reported. The pseudo-groups will be created using the binary indicators of diet, sleep, and physical activity.

Genetic information (via polygenic risk scores) will only be used in the analysis if it is feasible based on the available sample.

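### The LifeHD derivation models in Appendix C leave out the baseline value of the outcome, so factor selection and weights can partly reflect severity already present at baseline

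*SAP*

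**What the plan says.** Section 6.2 of the SAP gives the purpose of LifeHD: to "investigate the association of a lifestyle-based score with the progression of HD". Appendix C gives the algorithm.

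- Step 1 enters each risk factor separately in a regression "together with non-lifestyle factors: age, sex, HD stage, time since diagnosis, and follow-up time since last visit".
- Step 2: "Factors that were significant in the first step will be simultaneously placed into a single regression model". It does not say whether the Step 1 adjusters are kept.
- Step 3: "risk scores will be assigned for each factor with the respective β coefficients". Step 4 then rescales these coefficients by the smallest one.
- The outcome is a level, not a change: "as the outcome is cUHDRS or its components linear regression will be used". Section 6.1.5 says that these outcomes "will be assessed 12 months after the initial (baseline) assessment".

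Elsewhere the plan handles baseline differently. Section 6.2.1 lists baseline cUHDRS among the covariates for controlling confounding. Section 6.2.2 says: "Unweighted analyses (using regression models) will control for age, HD stage, as well as baseline values for the outcomes". It also attempts to balance baseline outcome values in the weighted analysis if sample size permits. Table 5 shows that cUHDRS and all four components are measured at baseline as well as at 12 months.

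**The concern.** A 12-month level without its baseline mixes where a participant started with how far he or she moved. If participants who were already worse at baseline also walk less or sleep less efficiently, a regression of the 12-month level on a lifestyle factor picks up that existing difference. It can then pass the Step 1 significance test and enter the score as a weight. The direction of inference may even be reversed, with severity driving lifestyle.

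The only direct severity adjuster in Step 1 is HD stage, which Table 4 defines as late pre-manifest plus three TFC bands. TMS, SDMT and SWRT are not banded in stages 1 to 3.

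Adjusting for baseline in the later LifeHD outcome analysis does not undo this, because the weights are fixed by then. Cross-fitting, which addresses deriving and testing a score on the same participants, would not remove it either.

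**Working it through.** The SAP gives no figure for this point, so there is nothing of its own to reproduce. The size is shown over a range of assumptions.

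**How much severity HD stage leaves open.** In the cUHDRS formula of section 6.1.3, TFC is divided by 1.9. Within stage 1 (TFC 11 to 13), TFC alone can move cUHDRS by 2/1.9 = 1.1 points; within stage 2 (7 to 10) by 3/1.9 = 1.6; within stage 3 (0 to 6) by 6/1.9 = 3.2. The other three components vary in addition.

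**Inputs for the selection rate.** From the SAP: n = 300 (section 3.3), significance level 0.05 (section 4.1) and a split at the lower tertile (section 6.2). Assumed: correlation c between the factor and baseline severity within a stage; correlation r between baseline and 12-month outcome within a stage; within-stage outcome SD of 1; a two-sided test; and no effect of the factor on progression.

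**Closed form.** For a standard normal variable split at its lower tertile, the two groups differ by φ(0.431)/(1/3 × 2/3) = 0.3636/0.2222 = 1.636 SD. The expected spurious coefficient is therefore c × r × 1.636. Its standard error with 100 and 200 participants is √(1/100 + 1/200) = 0.1225. The selection rate is approximately Φ(coefficient/0.1225 − 1.96).

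At c = 0.2:
- r = 0.5: coefficient 0.164, z = 1.34, selection about 27%.
- r = 0.8: coefficient 0.262, z = 2.14, selection about 57%.
- r = 0.9: coefficient 0.294, z = 2.40, selection about 67%.

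**Simulation.** 1,500 runs per cell, four equal stages, adjustment for age, sex and stage. Rate at which a factor with no effect on progression passes Step 1:

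| c | r = 0.5 | r = 0.8 | r = 0.9 |
|---|---|---|---|
| 0.1 | 10.6% | 18.2% | 21.7% |
| 0.2 | 25.4% | 53.8% | 64.4% |
| 0.3 | 49.1% | 88.1% | 95.3% |

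With the baseline outcome added, the rates are 4.3% to 5.3%. At c = 0.2 the mean spurious coefficients are 0.165, 0.261 and 0.300, which agree with the closed form.

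**A second simulation on the cUHDRS formula.** Here four components load 0.8 on a latent severity, stage is derived from TFC, the 12-month change has mean −0.9 and SD 1.2, and the factor correlates ρ with latent severity (2,000 runs). All of these values are assumed.

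| ρ | Selected, stage only, n = 300 | Selected, stage only, n = 210 | Coefficient without stage, n = 300 | Coefficient with stage, n = 300 |
|---|---|---|---|---|
| 0 | 4.8% | 5.4% | 0.00 | 0.00 |
| 0.2 | 33.3% | 24.6% | 1.04 | 0.49 |
| 0.3 | 63.8% | 47.6% | 1.55 | 0.74 |
| 0.4 | 86.4% | 71.6% | 2.04 | 0.97 |

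Coefficients are in cUHDRS points. The 210 is 70% of 300, the 12-month follow-up threshold in section 6.1.1. Stage removes about half of the spurious coefficient (1 − 0.49/1.04 = 53%). Adding baseline cUHDRS brings selection to 5.0% to 5.9% at n = 300 and 4.0% to 4.7% at n = 210.

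Neither simulation includes time since diagnosis or follow-up time.

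**The case against.** The strongest reply is that section 6.2.2 already states a general rule: unweighted regressions control for baseline outcome values. Steps 1 and 2 are unweighted regressions, and Appendix C does not say that its list of adjusters is exhaustive. On that reading only a cross-reference is missing. This is possible but not the natural reading. The same rule also requires adjustment for the other two lifestyle factors, whereas Step 1 enters risk factors one at a time. Step 1 also names sex, time since diagnosis and follow-up time, which section 6.2.2 does not. An analyst following Appendix C as written would leave baseline out.

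Three further objections stand in part.

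- A reader might infer that the weights measure severity and not progression at all. The plan does not support that. Step 1 adjusts for HD stage, age and time since diagnosis, and stage alone removes about half of the spurious coefficient in the second simulation. For the TFC model, where stages 1 to 3 are TFC bands, more of the baseline is already covered.
- A reader might set the spurious coefficients of 0.17 to 0.30 beside the 0.23 in section 3.3. That comparison is not valid. The 0.23 is per unit of a continuous predictor; these are contrasts between two groups in within-stage SDs. A tertile split has SD √(1/3 × 2/3) = 0.471, so they amount to about 0.08 to 0.14 per predictor SD.
- LifeHD is exploratory and secondary to the feasibility objective. The later unweighted LifeHD analysis falls under the baseline adjustment of section 6.2.2, so a false progression effect there does not automatically follow. What remains is a score whose content and weights are partly wrong for its purpose.

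**Conclusion.** The concern holds in a limited form. Appendix C derives LifeHD from a 12-month level without its baseline, which fits neither the stated aim of studying progression nor the baseline adjustment in sections 6.2.1 and 6.2.2. HD stage reduces the resulting bias but does not remove it.

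The direction is clear if lifestyle tracks severity within a stage; if it does not, there is no bias. The size cannot be fixed from the SAP, which gives neither the factor-severity nor the baseline-to-12-month correlation. Over the ranges assumed here, a factor with no effect on progression is selected in about 11% to 95% of runs at n = 300 without the baseline outcome, and in about 5% with it. The range is wide, and its upper end needs both correlations to be high. The point deserves correction before analysis, but it does not touch the primary feasibility outcomes.

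**What to change.** In Appendix C, Step 1, add the baseline value of the outcome being modelled to the adjusting factors: baseline cUHDRS for cUHDRS, and baseline TFC, TMS, SDMT or SWRT for the component models.

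In Step 2, state that this baseline value and the other Step 1 adjusters stay in the joint model. Say which terms are scored. The baseline outcome, sex, time since diagnosis and follow-up time are not scored. Age, HD stage and CAG remain scored, as section 6.2 and Table 4 intend. This needs to be explicit, because treating every adjuster as unscored would drop age and HD stage from the index.

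The cost is a few sentences and one covariate per model, using data already collected. There are three small downsides. Participants without a baseline outcome value need imputation or drop out of the derivation. Fewer factors may reach Step 2. The HD stage weight will change, because stage overlaps with baseline TFC and must then be read as given baseline.
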